5.2.2 Secondary endpoint

a- Comparison of the presence of EBV infection in the cohort of patients suffering from UC and divided into the following subgroups: a) new diagnosis; b) responders to conventional therapies; c) non-responders to conventional therapies, in order to unravel whether it is a bystander or causative of the onset/relapse of the disease and whether it is responsible for refractoriness to standard of care.

b- Evaluation of the diagnostic ability in detection of EBV infection of ISH performed on mucosal specimens with respect to qRealTime-PCR.

c- Evaluation of the diagnostic ability in detection of EBV infection between qRealTime-PCR performed on peripheral blood samples with respect to mucosal specimens.

d- Evaluation of association between mucosal/blood viral load and mucosal damage as endoscopically assessed (see paragraph 5).

e- Evaluation of association between clinical index of UC activity and EBV infection.

f- Evaluation of association between steroid therapy (absent, previous or current) and EBV infection.

g- Evaluation of association between immunosuppressive therapy (absent, previous or current) and EBV infection.

h- Evaluation of association between biological therapy (absent, previous or current) and EBV infection.

i- Evaluation of the prognostic role of EBV infection on the 6 and 12 months outcome (colectomy / number of hospitalization / cause of hospitalization).

5.2.3 Exploratory endpoints

- Identification of the life cycle phase of EBV infection through qRealTime-PCR and ISH. Specifically, the expression of EBER RNA will be assessed to distinguish between the lytic and latent phase of EBV infection into colonic specimens (31,39). In particular, although the presence of EBER is typically considered latency-associated, its expression was also found to promote cell growth and modulate innate immunity in EBV-associated epithelial cancers (31,40).

6 PATIENT SELECTION CRITERIA

For these purposes, a cohort of **100 patients with UC**, as diagnosed following the worldwide accepted criteria (2,41), either naïve or under standard of care (both responders and non-responders), will be prospectively enrolled. In all cases, the clinical and endoscopic indexes of activity will be carefully assessed. Specifically, to establish the refractoriness to current therapy, the following criteria will be applied: steroid-refractoriness is defined as the persistence of active disease despite an adequate dose and duration of steroid treatment (prednisone, 0.75–1 mg/kg day orally for at least two weeks; methylprednisolone, 1 mg/kg day intravenously for one week) (42); primary and secondary non-response to biological agents (infliximab, adalimumab, golimumab, vedolizumab) is considered as the lack of clinical improvement with induction therapy or recurrence of symptoms of disease activity during maintenance therapy despite an appropriate interval adjustment and dose escalation with exclusion of concomitant condition, respectively (43); resistance to immunosuppressive therapy (azathioprine, cyclosporine) on the basis of lack of clinical improvement after at least 4 weeks of treatment or the development of a flare of disease under appropriate maintenance dosage. For those patients following combination therapies, refractoriness is defined as the persistence of symptoms of active disease despite at least 4 weeks' treatment. In all cases, the Montreal classification is applied to assess the behavior, severity, and extent of the illness (44), while the clinical disease activity index is assessed according to the Simple Clinical Colitis Activity Index (SCCAI – Appendix 1) (45). Remission is defined as a SCCAI score of below 3 points. The endoscopic activity score is evaluated according to the Ulcerative Colitis Endoscopic Index of Severity (UCEIS – Appendix 2 - score ranging from 3 to 11, with a higher score indicating more severe disease) (46,47).

The **control group consists of 100 sex- and age-matched subjects**, selected in the same Center, undergoing colonoscopy with mucosal sampling as diagnostic workup for IBS in order to exclude macroscopic or microscopic disorders, or because alarm features are present: aged > 45-50 years, anemia, family history of colon cancer. That are confirmed to be suffering from IBS (C1), functional constipation/diarrhea (C2, C3) and functional abdominal bloating/distension (C4), following the Rome IV criteria (48), and who were not taking drugs possibly affecting immune response (steroids, immunosuppressant and biological agents) and microbiota composition (antibiotics, probiotics, prebiotics, proton pump inhibitors).

In addition, a small cohort of patients (n=20) suffering from **microscopic colitis** will be also enrolled as pathological control group (49).

All enrolled patients and controls undergo lower endoscopy with mucosal sampling and laboratory tests as diagnostic workup for their condition:

- Patients with active UC undergo colonoscopy and laboratory tests according to International guidelines and depending on physician judgement: active UC patients will undergo colonoscopy at baseline and laboratory tests at baseline, and at 3 and 6 months. A number of these patients, according to medical judgment, undergo medical examination at 9 and 12 months, and laboratory tests and colonoscopy at 12 months as optional follow-up. This is why the aim of the study is calculated at 6 months, but adding the optional follow-up at 9 and 12 months, will aid to understand if patients with superimposed EBV colitis undergo colectomy more frequently than patients without EBV colitis
- Patients with UC in remission undergo colonoscopy and laboratory tests as standard follow-up of their pathological condition according ECCO-ESGAR guidelines [52] (ex: to evaluate mucosal healing or screening)
- Patients with IBS undergo colonoscopy and laboratory tests only if alarm features are present (age > 45-50 years, anemia, family history of colon cancer, weight loss, blood mixed with stool).

Each enrolled case will undergo clinical and/or laboratory examination as standard follow-up of his/her pathological condition. All the laboratory tests are shown in the Appendix 5.

Each patient and control give written informed consent after approval by the local Bio-Ethics Committee is obtained.

6.1 Inclusion criteria

- ❖ Patients of either sex, aged 18-75 years (inclusive), without racial restriction.
- ❖ Patients undergoing colonoscopy with mucosal sampling.
- ❖ Ability to give informed consent according to International Conference on Harmonisation (ICH) Good Clinical Practice (GCP) and local regulations.
- ❖ Have given written informed consent to participate in the study before initiation of any study specific procedure.
- ❖ Prior and current standard treatments allowed.
- ❖ Diagnosis of UC according to the worldwide accepted criteria (2,41) (any age of onset, any localization, any activity of the disease, any severity of symptoms and signs of the disease).

6.2 Exclusion criteria

- ❖ Presence of significant comorbidities, such as uncontrolled hypertension and/or diabetes mellitus, invalidating psychiatric or neurological disorders, organ failure (renal impairment defined by creatinine clearance below 50 ml/min or by serum creatinine ≥ 2.0 mg/dl; hepatic impairment defined by total bilirubin ≥ 3.0 mg/dl and AST + ALT $\geq 2.5 \times$ upper normal value; cardiac failure with an output fraction $\leq 40\%$; respiratory insufficiency with a $pO_2 \leq 60$ mm Hg in arterial blood), or any other clinically significant condition, as determined by the Principal Investigator.
- ❖ Primary immunodeficiencies and human immunodeficiency virus infection.
- ❖ Pregnancy.
- ❖ Known malignancy.
- ❖ Patient who has had abdominal surgery, either open or laparoscopic, within the 3 months prior to screening.
- ❖ Patient recruited in another trial.
- ❖ Patient with a positive test for active hepatitis B or C disease or active severe infections.
- ❖ Known history of alcohol or drug abuse in the 12 months prior to inclusion.

7 STUDY DESIGN

This is an investigator-initiated prospective multicentre interventional without drug and medical device study evaluating the prevalence, role, life phase and the most accurate diagnostic method of EBV infection in UC. A longitudinal study is included to assess whether EBV infection has an impact on patients' outcome (see Appendix 3 illustrating the time points of the study).

7.1 General design

- ❖ *Type:* cross-sectional study with a longitudinal component.
- ❖ *Description of the exposure of interest:* EBV infection, defined as isolation of the EBV or detection of viral proteins or nucleic acids in any body fluid or tissue specimens.
- ❖ *Description of the matching factor(s) and how the matching will be done:* Center, sex- and age (5 year classes)-matching will be performed among the IBD patients and concomitant non-IBD control subjects.
- ❖ *Methods used to minimize bias.* The assessment of EBV infection through qRealTime-PCR, histology or ISH as primary endpoint is *per se* unbiased due to standardization and reproducibility of the techniques applied. Also calculation of clinical and endoscopic indexes of activity are routinely applied in IG-IBD centres. Moreover, the measurement of exploratory endpoints will be assessed by blinded technicians, whereas monitoring of patients' outcome will be performed by the local Principal Investigator.
- ❖ *Describe the strategy/process by which participants will be recruited, screened, and enrolled in the study.* All cases admitted at each IG-IBD center that agrees to participate in this study will be screened for inclusion. All enrolled cases undergo lower endoscopy with mucosal sampling from both inflamed and non-inflamed mucosa in each IBD patient and from healthy mucosa in each control subject, as part of their diagnostic workup for disease diagnosis, relapse or follow-up. Patients' assessment includes: clinical examination, body mass index calculation, evaluation of smoking habits and stratification according to the Montreal classification (44), routine laboratory tests, and calculation of clinical [SCCAI (45)] and endoscopic [UCEIS (46,47)] indexes of activity.
- ❖ All enrolled cases also undergo peripheral blood harvest. Quantitation of viral DNA load will be performed on both peripheral blood samples and whole mucosal specimens by means of qRealTime-PCR (50). In addition, mucosal specimens will be also evaluated by ISH.

- ❖ Quantitation of EBV and HCMV DNA. For each patient and control, the EBV and HCMV load will be assessed in terms of International Units (IU) on both freshly collected whole peripheral blood samples and endoscopic specimens harvested from colonic mucosa, by qRealTimePCR technique as previously reported (51). Specifically, in the IBD group, two snap-frozen biopsies will be taken from either inflamed and/or non-inflamed mucosa as assessed during the endoscopic examination, that is from the edge of the ulcers and the nearby damaged zones for the former and at least 20 cm away from the affected areas for the latter. Two snap-frozen biopsies from healthy mucosa (possibly transverse colon) will be collected from each non-IBD patient. Viral DNA extraction will be performed by using the EZ1 DNA Tissue kit and EZ1Virus Mini Kit v2.0 (Qiagen, Hilden, Germany), while EBV DNA will be quantified by using the artus EBV QS-RGQ PCR Kit (Qiagen), and HCMV DNA will be quantified by using the artus CMV QS-RGQ kit (Qiagen), according to the manufacturer's instructions. Results will be expressed as IU/ml of blood and IU/10⁵ cells. Normalization of viral DNA load in tissue samples will be obtained by quantitative determination of β_2 -microglobulin gene. The lower detection limit is 1 DNA input target DNA copies (51). This analysis will be carried out at the the Molecular Virology Unit in Pavia.
- ❖ In situ chromogen hybridization. Mucosal specimens harvested in parallel from the same areas as those for the qRealTimePCR assay and needed for traditional diagnostic immunohistochemistry, will be fixed in 10% neutral buffered formalin and paraffin-embedded. Sections (4 μ m) will be transferred to pre-treated glass slides (DAKO, Denmark) and stored at 37°C overnight. The haematoxylin-eosin staining will be performed following standard protocol, while the specific *in situ hybridization* for EBV will be carried out on seriate sections. Briefly, the slides will undergo enzyme pretreatment (Leica AR9551) for 30 minutes at room temperature, and then hybridized with a FITC-labeled peptic nucleic acid probe complementary to EBV-encoded RNAs (EBER-PROBE; Leica) and incubated overnight at 55°C. After washing in restricting conditions for 35 minutes, the hybridized cells will be visualized with an ISH detection kit (Leica DS AR0833 and then 9800) according to the manufacturer's instructions. The sections will be then counterstained with Kernechtrot, dehydrated through graded alcohols, immersed in xylene and mounted with a permanent medium. The present ISH method stain the nuclei of EBV infected cells dark blue, whilst the nuclei of non-infected cells appear red. This analysis will be carried out at the Service of Pathology, ASST Spedali Civili (Brescia).

Protocol code: REBUC
Effective date: 03/10/2022
Version no: 4.0
Page 23 / 50

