Population and patient selection criteria

A cohort of 100 adults (18-75 years) patients with UC, either naïve or under standard of care (both responders and non-responders to therapies) will be prospectively enrolled. In all cases, the Montreal classification, and the clinical and endoscopic indexes of activity will be carefully assessed. The control group consists of 100 sex- and age-matched subjects, selected in the same Center, undergoing colonoscopy as examination in the diagnostic algorithm for lower abdominal symptoms and **that results normal, thus confirming the diagnosis of** irritable bowel syndrome, and who were not taking drugs possibly affecting immune response and microbiota composition. **A small cohort of patients (n=20) suffering from microscopic colitis will be also enrolled as pathological control group.** All enrolled patients and controls will undergo lower endoscopy with mucosal sampling as **diagnostic** workup for their condition. Patients with active UC undergo colonoscopy and laboratory tests according to international

guidelines and depending on physician judgement. More in depth, active UC patients will undergo colonoscopy at baseline, while laboratory tests will be performed at baseline, and at 3 and 6 months. As optional follow-up, accordingly with physician evaluation, some patients will undergo medical examination and laboratory tests at 9 and 12 months, and colonoscopy at 12 months. The aim of the study is settled at 6 months, but adding the optional follow-up at 9 and 12 months, will aid us to understand if patients with EBV colitis undergo colectomy more frequently than patients without EBV colitis. Patients with UC in remission will undergo colonoscopy and laboratory tests according to ECCO-ESGAR guidelines [52]. Patients with suspicion of irritable bowel syndrome will undergo colonoscopy and laboratory tests if alarm features are present (aged >45-50 years, anemia, weight loss, familiar history of colon cancer, blood mixed in the stool). The exclusion criteria include: significant comorbidities, malignancy, pregnancy, organ failure, immunodeficiencies, active infections, recent abdominal surgery, or invalidating psychiatric-neurological disorders.

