- ❖ Our previous studies have clearly showed the need for quantitative real time polymerase chain reaction (qRealTime-PCR) analysis performed on mucosal samples not only for its better diagnostic accuracy in comparison to *in situ* hybridization (ISH) and immunohistochemistry, but mostly in order to stratify the patients, since a positive result does not necessarily imply that the patient is suffering from an EBV-related end-organ disease (35). Indeed, we identified a cutoff of 1000 copies/100.000 cells as the value to distinguish a superimposed viral colitis from a pure relapse of the underlying disease (35). Furthermore, since no efficacious therapy is currently available for symptomatic EBV infection, the only possible intervention consists of a quick tapering and then discontinuation of steroids, while improving malnutrition if present. By contrast, the immunosuppressive and biological agents could be continued by virtue of their long-lasting effects. We also suggested a note of caution in prescribing steroids and biologics in those patients carrying a mucosal viral load of between 100 and 1000 copies, who should be closely monitored, while no modification of the standard treatment is needed for those with a mucosal viral load lower than 100 copies (36). In this regard, it should be emphasized that the search for circulating class M specific anti-virus antibodies is rather ineffective in detecting an active disease, since elevated levels can persist for up to two years after infection, while immunocompromised patients may not mount an IgM response (37).
- ❖ In addition, our evidence of localization of virus infection in colocytes represents the first step towards understanding the mechanisms of viral dissemination and the role of the lytic phase in tissue damage (24). Indeed, a suggested viral tropism to sites of inflammation, and its

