8.2 Analysis

Data will be described with the mean and standard deviation or the median and 25th-75th percentiles if continuous and as counts and percent if categorical. For the primary endpoint we will compute the prevalence as the ratio of the number of patients diagnosed with EBV infection to the number of patients evaluated, together with its 95%CI. We will use the Fisher exact test to compare the prevalence in UC patients to that of control. We will report the mean difference in proportions and its 95%CI. We will use binomial regression models with identity link (command binreg in Stata), to adjust for potential confounders, such as, but not limited to, age, gender, duration of disease and treatment. We will apply the 1:10 rule to adapt the number of confounders evaluated to the sample size. We will compare the prevalence of EBV infection between UC subgroups with the Fisher exact test (EP2a). In these cases, given in particular that the ratio of responders to non-responders is at yet unknown, we will compute *a posteriori* the power for the comparison. We will compute

sensitivity, specificity, area under the ROC curve and predictive values with 95% CIs for EP2b and EP2c. We will use the Spearman R and the Fisher exact test to assess the association, for continuous and categorical independent variables, respectively, with the dependent variables of EP2d to EP2h. All estimates will be presented with their 95% CI.

We will use Cox regression to assess the association of EBV infection with colectomy and of hospitalization for any cause; we will use Poisson regression to assess the association of EBV infection with the number of hospitalization from any cause. For secondary endpoints assessing associations, we will also fit regression models to adjust for possible confounders (as for the EP1) and report adjusted mean differences in proportions and 95% CI. We may also use propensity score inverse probability weights to account for the bias by indication when assessing treatment effect on the outcome.

The exploratory endpoints will be only descriptive.

We will use Stata 17 or later versions for computations. A 2-sided p-value <0.05 will be considered statistically significant. We will apply the Bonferroni correction for post-hoc comparisons.

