9 WITHDRAWAL OF SUBJECTS

It is under the responsibility of the Principal Investigator in each IG-IBD Centre who has in charge the patient to withdraw her/him from the study and to advise both the Study Coordinator and Data Manager specifying the reason/s. The impossibility to harvest mucosal biopsies is considered a criterion for subject withdrawal. In this case, the patient's data will be removed from the database, but considered when assessing patient disposition. The development of malignancy or death are primarily considered as evolution of the underlying disease. In addition, a patient has the right to withdraw from the study at any time for any reason. Subjects who withdraw their consent are considered withdrawn from the study. The Principal Investigator has the right to terminate participation of any patient if it is deemed in the patient's best interest and if she/he develops severe psychiatric or neurological disorders. The reason and circumstances for premature discontinuation must be reported in the patient's electronic case report form (eCRF). This means that a patient may be withdrawn in every phase of the trial, from the inclusion to any time of the follow-up period. In summary, reasons of withdrawal include, but are not limited, to the following:

- Patient's decision,
- Withdrawal of patient consent to participate in the study,
- Physician's decision based on patient's well-being.

For any subject discontinuing the study the Principal Investigator should before do the following:

- Complete the eCRF, indicating in the final visit, the date of termination and the reason for discontinuing the study as well as the protocol deviation section, with all data not corresponding to a formal visit filled in the Early Termination visit.

In patients who do not come back for the scheduled study visits, documented efforts should be performed to convince she/he to continue attending study visits and if unsuccessful, at least the exact reason(s) should be obtained for their discontinuation and any adverse event associated to it should be recorded.

The patient will be replaced if her/his mucosal specimens are not available for the full analyses.

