- *On-line test results (especially if only held electronically),*
- *Samples log.*

e) Database Access. Access to the eCRF database will be allowed to the Principal Investigators, data managers, members of the Steering Committee and IGIBD Scientific Committee. Any entry in the database will be traceable through its identification and date. Audit trail of data changes will be assured.

f) Data reported in the eCRFs should be consistent with and substantiated by the subject's medical record and original source documents. The final, completed eCRF Casebook for each subject will be electronically signed and dated by the investigator of the IG-IBD Centre to signify that the Investigator has reviewed the eCRF and certifies it to be complete and accurate within a month.

g) Data Queries. Data query forms will be generated to the Coordinator Investigator in order to clarify the data inconsistencies through the source data verification. Only then and after all detected errors, inconsistencies or doubts cleared, will the database declared a clean file and protected accordingly. IGIBDReg integrates a query management system.

h) All data entry, modification or deletion will be recorded automatically in an electronic audit trail. The investigators will retain all copies of the eCRF in the relevant sections of their Investigator Site File with any required anonymised background information from the medical records as required.

i) Clean File. A clean file will be created and registered, to which further changes will be disallowed. The database lock report will be generated which includes the eligibility of patients.

j) Data Quality Assurance. Periodic monitoring will be made by remote for source data verification, and to check compliance with the protocol, GCP and applicable regulatory requirements by the Data Manager. Quality control steps will be taken for the analytical protocol, results, and report.

k) The Trial Statistician will retain the final eCRF data and audit trail as permanent records of the study. A copy of all completed eCRFs will be provided to the investigators. Study document will be retained for 10 years after the completion of the protocol.

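### The prognostic endpoint (secondary endpoint i) is exposed to bias: outcomes are monitored by an unmasked treating investigator, and 12-month follow-up is chosen by physician judgement

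*Protocol*

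**What the plan says.** Protocol section 5.2.2, endpoint i, asks for the prognostic role of EBV infection on colectomy and on the number and cause of hospitalisations at 6 and 12 months. Section 8.2 gives the analysis: "We will use Cox regression to assess the association of EBV infection with colectomy". Admission for any cause is handled in the same way, and a Poisson model is added for the number of admissions.

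Section 7.1 lists its safeguards under methods to minimise bias. Blinding appears once: "the measurement of exploratory endpoints will be assessed by blinded technicians". The same sentence then says that monitoring of the patients' "outcome will be performed by the local Principal Investigator".

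That investigator's other functions are set out elsewhere:

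- Care and withdrawal (section 9, on withdrawing a subject): "It is under the responsibility of the Principal Investigator in each IG-IBD Centre who has in charge the patient".
- Data entry (section 10 a and f): the Principal Investigators fill in the eCRF directly, and the site investigator certifies each casebook.
- Access (section 10 e): "Access to the eCRF database will be allowed to the Principal Investigators, data managers, members of the Steering Committee". The scientific committee is also named, and no field is excluded.

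On follow-up, the Summary says: "As optional follow-up, accordingly with physician evaluation, some patients will undergo medical examination". This refers to the visits at months 9 and 12, with blood work at both and an endoscopy at the second. Section 6 repeats the option for active UC and says the optional visits will help to show whether patients with superimposed EBV colitis come to colectomy more often. Section 10 n says that if clinical, endoscopic and histologic data are missing by month 12, the outcome cannot be evaluated.

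**The concern.** An exposure-outcome comparison is protected when the people who manage, follow and record the patient do not know the exposure, or when outcomes are collected in the same way whatever they know. The plan states neither for endpoint i. It places its only blinding on the exploratory endpoints, which section 8.2 says will be descriptive only. It leaves unmasked the endpoint that is tested with Cox and Poisson models.

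There are two routes to bias. First, a known EBV result can change care or the threshold for admission. Section 3 shows that the investigators regard the result as actionable: for symptomatic EBV infection it says that "the only possible intervention consists of a quick tapering and then discontinuation of steroids", with attention to malnutrition, and it links an intermediate mucosal load to closer monitoring. Second, a known result can influence who is offered the 9- and 12-month visits, and so who contributes to the 12-month comparison.

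At stake is the reading of endpoint i. Section 3 says the study should settle whether EBV causes tissue damage or marks severe colitis. A difference in colectomy or admissions between EBV groups would mix the virus with the response of clinicians who know the result. The bias could hide a true association or create a false one.

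**Working it through.** The plan gives no power, event rate or precision for endpoint i. The sample-size table in section 8.1 concerns prevalence only, so there is no figure of the plan's own to reproduce. The check sets the passages side by side and then asks when selective 12-month follow-up would matter.

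**1. Is EBV status masked from the person who treats and records?**

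- Section 7.1 blinds only the technicians for the exploratory endpoints.
- Section 10 c says the database collects all clinical and other study data. EBV results are not named, so their inclusion is inferred.
- Section 10 e gives Principal Investigators access without restriction.
- Section 11.2 limits consultation of an anonymised upload by committee members and coordinating investigators. It does not restrict a site's access to its own eCRF.
- Viral load and ISH are measured centrally (sections 7.1 and 10). The timing and route of return to sites are not stated.
- Anti-EBV serology is a listed laboratory test (Appendix 5), and section 10 d has laboratory tests evaluated at the treating centre.

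Result: no masking is stated and one EBV-related result is available at the site by design. Disclosure of the central qPCR and ISH results is possible but not established.

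**2. Is follow-up uniform?**

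- Appendix 3: for active UC, 3 and 6 months are mandatory; 9 and 12 months are optional.
- Appendix 4: UC in remission has screening and baseline only, so the scheduled follow-up for endpoint i covers active UC.

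Result: uniform to 6 months in active UC, physician-selected after that.

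**3. When would selection at 12 months bias the comparison?** Let r be the true 12-month colectomy risk in one EBV group, a the chance of being followed for a patient who has a colectomy, and b the chance for one who does not. Among those followed:

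observed risk = r·a / [r·a + (1 − r)·b], so observed odds = true odds × (a/b).

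The observed odds ratio is therefore the true odds ratio × (a/b in EBV-positive) / (a/b in EBV-negative). If a/b is the same in both groups there is no distortion. If it differs, there is.

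The values below are assumed, with equal true risk in both groups (r = 10%, then the range for r from 5% to 20%). They show the condition and the direction and are not estimates for this study.

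| Assumed follow-up (a, b) | EBV+ observed | EBV− observed | Risk ratio at r = 10% | Range |
|---|---|---|---|---|
| EBV status only: + 0.8, 0.8; − 0.5, 0.5 | 10% | 10% | 1.0 | 1.0 |
| Course only: both 0.9, 0.6 | 14.3% | 14.3% | 1.0 | 1.0 |
| Joint: + 0.9, 0.9; − 0.9, 0.4 | 10% | 0.09/(0.09 + 0.36) = 20% | 0.5 | 0.47–0.56 |
| Joint: + 0.9, 0.4; − 0.7, 0.7 | 0.09/(0.09 + 0.36) = 20% | 10% | 2.0 | 1.8–2.1 |

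Result: with equal true risks, selection matters only if follow-up depends jointly on EBV status and course. It can then act in either direction. An unmasked physician choosing visits on judgement is the setting in which that joint dependence can arise.

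**4. Does the planned analysis repair it?** The propensity weights in section 8.2 are optional and aimed at bias by indication in treatment effects. They do not address care or follow-up prompted by a known EBV result. Adjustment for treatment as a confounder does not help where the treatment change itself follows from that knowledge.

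**The case against.** The strongest reply is that the key link is inferred. The assays are central, samples are stored before shipping, and the protocol never says that results return during follow-up or enter the eCRF. EBV-guided care appears only in the background; sections 6 to 8 prescribe none. The optional visits are left to the physician or to medical judgement, not to the Principal Investigator by name. The study aim is set at 6 months, where visits in active UC are mandatory. Colectomy is a hard event. The models use admission for any cause, so unblinded judgement of cause does not enter them. Charts and medical files are already source data checked by the Data Manager.

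Most of this stands. A reader might infer that the endpoint is contaminated, or that the aim of separating cause from marker cannot be met. The document supports neither: it shows an open route, not that the route is used. Nor can a reader say that treatment changes after a result go unrecorded, because section 10 a lists concomitant treatment among the data checked and the eCRF (Annex 2) is not shown.

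What the reply does not answer is that nothing closes the route. The 12-month set is physician-selected, the admission decision is itself open to influence, and source verification checks what was entered, not whether every patient was ascertained to 12 months.

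**Conclusion.** The point holds as an exposure to bias in one secondary endpoint. The role that has the patient in charge also fills in the eCRF, has database access with no stated masking of EBV results and monitors outcomes, while follow-up beyond 6 months is discretionary.

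The exposure is greatest for the 12-month reading and for admissions. It is smaller for colectomy at 6 months, where unequal visits are not planned and only altered care remains as a serious route. The primary prevalence endpoint is unaffected.

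No size is claimed. The document gives no event rates, no proportion followed to 12 months and no release rule for results. The conclusion rests on two assumptions: that EBV results can reach the site during follow-up, which is not excluded, and that knowing them could alter care or follow-up, which section 3 makes plausible. If the sponsor can show that results are withheld until follow-up ends, the concern about masking largely falls away, apart from local serology. Discretionary 12-month follow-up would still need uniform ascertainment.

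**What to change.** 1. In sections 7.1 and 10 e, state that the centrally measured research qPCR and ISH fields are hidden from the site role until that patient's last outcome form is signed. Any result requested for the patient's care is still released, and the release is logged.
2. Add an eCRF field for the date on which any EBV result became known to the site. This also covers what masking cannot, such as serology read locally.
3. Ascertain colectomy and admissions, with dates, at 6 and 12 months from hospital records for every active UC patient, whether or not the optional visits take place, using the source verification already planned. Amend section 10 n so that a missed month-12 visit does not by itself make these two outcomes unevaluable.
4. Describe endpoint i as an association under routine, possibly EBV-informed care.

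An analysis that censors follow-up at the first treatment change after disclosure should not be added. Treatment tends to change when patients deteriorate, so that censoring would be informative.

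The cost is one database permission, one eCRF field, a record check at two time points and a few sentences of text. It needs no extra staff or patient procedures. The downside is that routine display of research results to sites is delayed.
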